6.5 Pooling of Centers

Sites will be pooled as follows: US sites and Rest of the World sites, for the analysis of the primary and secondary efficacy endpoints.

7 DEMOGRAPHIC, OTHER BASELINE CHARACTERISTICS AND MEDICATION

7.1 Subject Disposition and Withdrawals

The disposition table will include the number of subjects present at each phase, and discontinued along with the reason for discontinuation. Data will be summarized by cohort, treatment, phase, and period, as appropriate.

Additionally, duration in study will be summarized.

7.2 Demographic and Other Baseline Characteristics

Subject demographic data (age, gender, race, and ethnicity), height, weight and body mass index (BMI) will be collected at study screening and will be summarized by using descriptive statistics by cohort and overall.

Height (in cm) = height (in inches) * 2.54

Weight (in kg) = weight (in lbs) * 0.4536

BMI (kg/m²) = Weight(kg)/(Height[m]²)

7.3 Medical History

Medical history will be listed. The medical history conditions will be summarized for each of the 4 periods within the 2 phases and cohorts combinations by treatment group and overall using frequencies and percentages on the body system levels and preferred term. Medical history will be sorted alphabetically by body system and preferred term. Medical history terms were coded using MedDRA version 16.0.

7.4 Epilepsy History

Epilepsy history will be documented via eCRF at screening and includes the following information: age in years and in months at first seizure, followed by the family history(Y/N) in first degree relatives (parent, sibling, and child). For each 'Y', the following are collected: seizure type (if applicable and known), IQ (with date), Neurological Dysfunction. Additionally, seizure calendars will be collected at the each visit and includes the following: date and type for each seizure. These data will be summarized via appropriate summary statistics (see [Section 6.1](#)), and will be listed. Percentage of patients with VNS will be summarized.

7.5 Medication

Subjects participating in the study must be taking 1-3 AEDs in addition to the investigational medication. Marketed medications indicated for the treatment of partial seizures are acceptable with the exceptions noted below:

Vigabatrin: Current use of vigabatrin (Sabril) is not permitted for the duration of the study due to its ophthalmologic toxicity, as well as prior use of vigabatrin without stable visual fields tested twice over the 12 months after the last dose of vigabatrin.

Ezogabine (retigabine; Potiga; Trobalt): Current use of ezogabine (retigabine) is not permitted. Subjects who may have used this agent in the past should have been off this medication for at least 3 months prior to screening and should have had a documented normal fundoscopic exam by an ophthalmologist.

Perampanel (Fycompa): Perampanel is permitted as a concomitant medication only if the subject has been on a stable dose for at least 3 months prior to screening and has not experienced any serious psychiatric and behavioral reactions and is expected to remain on a constant dose throughout the study.

Felbamate: Felbamate (Felbatol) is permitted as a concomitant medication only if the subject has been on felbamate for at least 18 months and has stable AST/ALTs and hematology laboratory tests and is expected to remain constant throughout the study.

Benzodiazepines: If a subject is taking a benzodiazepine chronically for epilepsy and/or non-epilepsy conditions, it will be counted as 1 of the 3 AEDs and the dose cannot be changed during the study.

Vagal Nerve Stimulator: Subjects receiving treatment with a VNS may be included as long as the VNS has been in place for at least 1 year prior to entry into the study, the VNS battery is not due for replacement during the DB phase (Cohort 1 weeks 1 to 9 and Cohort 2 weeks 1 to 14), and stimulation parameters have been kept constant for 3 months prior to screening. VNS will not be counted as one of the 3 concomitant AEDs.

AED medications will be coded using WHODrug Dictionary (December 2013), and will be summarized by standard medication name and medication class and sorted by descending incidence of standard medication name then alphabetical within medication class. Data listings will be sorted in the same manner.

The following table describes how missing date information regarding AED medications will be handled

Partial Missing Start or Stop Date	Imputed Start Date	Imputed Stop Date
Missing month and day, and the year is present	January 1 of that year or first dose date if the year is the same as the year of first dose date	December 31 of that year
Missing day, but year and month are present	First day of that month or first dose date if the year and month are the same as the year and month of first dose date	Last day of that month
Missing month, but year and day are present	Missing month imputed as January	Missing month imputed as December

7.5.1 Prior Medication

Prior medications will be summarized by WHO Drug Dictionary (December 2013) standard medication name, cohort, and treatment group. Prior medication will be listed. Prior AED medications will be summarized separately.

A prior medication will be defined as any drug that has a start date before the first dose date of study drug. Any medication that starts on the first dose date of study drug will not be considered prior. Medications with a completely missing start date will be considered prior.

Partial start dates will be used to determine if a medication is prior. Medications with a completely missing start date will be considered prior. If only a start month and year are present, then medications for which the month is before or the same as the first dose month will be

considered prior. If only the start year is present, then medications for which the start year is before or the same as the first dose year will be considered prior.

7.5.2 Concomitant Medication

Concomitant medications will be summarized by WHO Drug Dictionary (December 2013) standard medication name, cohort, treatment phase and treatment group. Concomitant AED medications will be summarized separately. Concomitant medication will be listed.

Concomitant medications will be defined as any drug that has a start date on or after the first dose date of study drug. A medication that starts prior to first dose and stops after first dose will be considered as both Prior and Concomitant medications. Medications with a completely missing end date will be considered concomitant.

8 EFFICACY

8.1 Primary Efficacy Endpoint and Analysis

The primary efficacy endpoint for US FDA registration is the percent change in 28-day seizure frequency (POS with or without secondary generalization) in Cohort 2 DB phase (14-week titration + maintenance treatment periods) relative to the baseline in the MITTP, frequency of POS seizures only includes 3 seizure subtypes which are SPS-motor, CPS and SGTC. Post-baseline 28-day seizure frequency will be calculated as the number of seizures in the entire treatment phase divided by the number of days with available seizure data in the treatment phase, multiplied by 28. Baseline 28-day seizure frequency will be calculated as the number of seizures in the baseline period divided by the number of days with available seizure data in the baseline period, multiplied by 28. The calculation for percent change from baseline in 28-day seizure frequency will be done as follows for each subject:

$$\left(\frac{[(\text{Post-baseline 28-day seizure frequency}) - (\text{Baseline 28-day seizure frequency})]}{(\text{Baseline 28-day seizure frequency})} \right) \times 100\%$$

The baseline, post-baseline, and percent change from baseline in 28-day seizure frequency will be summarized by treatment group using descriptive statistics.

The null hypothesis is that there is no difference in the medians between the 2 treatment groups with respect to percent change in seizure frequency.

A rank analysis of covariance (ranked ANCOVA) will be used as primary analysis. A nonparametric rank analysis of covariance will be used to analyze rank of percent change data from baseline, with treatment and pooled center (either US or ROW) as factors and the rank of baseline 28-day seizure frequency as a covariate in the model. The baseline, post-baseline, and percent change from baseline in 28-day seizure frequency will be summarized by treatment group by using descriptive statistics. The 2-sided significance level of 0.05 will be used for comparison. Hodges–Lehmann estimator and 95% confidence interval (CI) for the estimator will be calculated.

An analysis of covariance (ANCOVA) as a sensitivity analysis will be conducted on the rank of percent change data from baseline, with treatment and pooled center (either US or ROW) as factors and the rank of baseline seizure frequency as a covariate. *P*-value to test treatment effect will be determined by permutation test with seed = 123456 and 2000 iterations. To deal with the missing data after subjects dropout, the multiple imputation method described in [Section 6.3](#) will be utilized to perform additional sensitivity analyses. These analyses provide a robustness assessment of the results.

The MITT population of Cohort 2 is the primary population for efficacy analysis. The PP population of Cohort 2 will be considered as supportive.

There are 2 different types of baselines in the study; Cohort 1 has a baseline composed of 4 weeks retrospective + 4 weeks prospective data collection, while subjects in Cohort 2, randomized under protocol amendment 3, has a baseline composed of 8 weeks of prospective data collection; however subjects randomized under protocol amendment 2 will have baseline data that is collected in the same fashion as Cohort 1 subjects. Summary statistics will be generated by type of baseline to provide information regarding the robustness of the endpoint with respect to the choice of baseline. Wilcoxon rank sum test will be used to test if there is difference between these 2 types of baseline. Hodges–Lehmann estimator and 95% confidence interval (CI) for the estimator will be calculated.

For European (EMA) Registration

The primary efficacy endpoint for EMA registration is 50% responder rate during the maintenance treatment phase of DB phase for Cohort 2. A 50% responder is an individual who experiences at least a 50% decrease in seizure frequency compared to baseline. This end-point is analysed independently of the FDA registration end-point, and analysis of the key secondary end-points (below) is not predicated on the results of this end-point.

The responder rates between ganaxolone and placebo will be compared using a logistic regression model, with terms for treatment, pooled center (either US or ROW), and baseline 28-day seizure frequency in the model. The number and percentage of responders will be summarized by treatment, odds ratio and associated 95% confidence interval and p-values will be reported.

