
Criteria for Efficacy Evaluation: The primary efficacy endpoint for US Food and Drug Administration registration is the percent change in the 28-day seizure frequency (POS with or without secondary generalization) from baseline to the DB phase for Cohort 2. The primary endpoint analysis will consist of rank analysis of covariance (ANCOVA) conducted on the percent change data, with treatment and pooled countries as factors and the rank baseline seizure frequency per 28 days as a covariate
 
The primary efficacy endpoint for European registration is 50% responder rate during the maintenance treatment phase of the double-blind phase for Cohort 2. A 50% responder is an individual who experiences at least a 50% decrease in seizure frequency compared to baseline.
 
Key secondary end-points
 
The three key secondary endpoints will be tested using a fixed sequence procedure to protect the familywise error rate at 0.05. If the primary outcome measure is statistically significant, the p-values of the secondary measures will be examined in the order listed below. The process stops at the first p-value above 0.05.
 
• Responder rate (experiencing a $\geq 50\%$ reduction) during the titration + maintenance treatment periods of the DB phase for Cohort 2• Change in the number of seizure free days per 28-day period from baseline during the titration + maintenance treatment periods of the DB phase for Cohort 2• Clinical Global Impression of Change – Improvement (CGI-I; Investigator) at Week 14 of the double blind treatment phase relative to the baseline for Cohort 2

All remaining secondary efficacy endpoints listed in the protocol will be tested at alpha =.05 so all p-values are nominal.

Secondary efficacy outcome measures are listed below.

- a) Percent change in the 28-day seizure frequency from baseline to the DB phase during the maintenance treatment period for Cohort 2
- b) Change from baseline in 28-day seizure frequency during the DB phase for Cohort 2 (titration + maintenance and maintenance only).
- c) Change in the number of seizure free days per 28-day period from baseline during the maintenance treatment period of the DB phase for Cohort 2
- d) Proportion of responders experiencing a $\geq R\%$ reduction from baseline to the end of treatment period in 28-day seizure frequency (titration + maintenance and maintenance only) for Cohort 2. R% will be 20%, 40%, 60%, and 80%

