6. INVESTIGATORS AND STUDY ADMINISTRATIVE STRUCTURE

This will be a multi-center study with approximately 55 investigational sites in the USA, the Russian Federation (Russia), Australia, Bulgaria, Germany and Poland with approximately 6 subjects enrolled at each site. Study enrollment is planned for 26 months from the time of first subject visit. Duration of subject participation in Cohort 1 is up to 67 weeks: 4 weeks prospective seizure recording, 1 week titration, 8 weeks double-blind maintenance (total 9 weeks of double-blind [DB] treatment), 52 weeks of additional open-label (OL) treatment \pm 2 weeks of dose de-escalation at study end. Duration of subject participation in Cohort 2 is up to 76 weeks: 8 weeks prospective seizure recording, 2 week titration, 12 weeks double-blind maintenance (total 14 weeks of double-blind [DB] treatment), 52 weeks of additional open-label (OL) treatment \pm 2 weeks of dose de-escalation at study end.

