9.7 Statistical Methods Planned and Determination of Sample Size

9.7.1 Randomization

Subjects will be randomized to receive ganaxolone or placebo during Phase 1 in a 1:1 ratio by the interactive web response system (IWRS) system. Randomization for Cohort 2 will be stratified by country.

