9.7.5 Analysis of the Primary Efficacy Variable

The primary efficacy measure is the percentage change in seizure (POS with or without secondary generalization) frequency per 28 days in the Cohort 2 double-blind period 14-week titration + maintenance period relative to baseline in the mITT analysis. Seizure frequency will be based on the number of seizures per 28 days, calculated as (the number of seizures over the time interval multiplied by 28) and divided by the number of days in the interval.

The hypothesis for percent change in seizure frequency per 28 days is:

$$H_0: \mu_1 - \mu_2 = 0 \qquad H_a: \mu_1 - \mu_2 \neq 0$$

where μ_1 and μ_2 are the median percent change in seizure frequency.

A rank analysis of covariance (ANCOVA) will be conducted on ranked percent change data, with treatment and country as factors and the ranked baseline seizure frequency per

28 days as a covariate. The p-value based on the rank ANCOVA will be presented.

Hodges-Lehmann estimator and its 95% confidence interval (CI) will also be calculated.

An analysis of covariance (ANCOVA) as a sensitivity analysis will be conducted on the rank of percent change data from baseline, with treatment and pooled center (either US or ROW) as factors and the rank of baseline seizure frequency as a covariate. P-value to test treatment effect will be determined by permutation test with seed=123456, and 2000 iterations. This analysis provides a robustness assessment of the results.

The primary efficacy endpoint for European Medicines Agency registration is 50% responder rate during the maintenance treatment period of the DB phase for Cohort 2. A 50% responder is an individual who experiences at least a 50% decrease in seizure frequency compared to baseline. This end-point is analyzed independently of the US registration end-point. The key-secondary end-point analysis (below) is not predicated on the results of this end-point.

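### The SAP adjusts the primary rank ANCOVA for US versus rest of world, Protocol 9.7.5 for country (the randomisation stratum); the change is undeclared and no SAP sensitivity analysis adjusts for country

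*SAP*

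**What the plan says.** - **SAP 8.1, primary model:** "with treatment and pooled center (either US or ROW) as factors and the rank of baseline 28-day seizure frequency as a covariate". SAP 6.5 applies the same two-level pooling to all primary and secondary efficacy endpoints.
- **Protocol 9.7.5, primary model:** "with treatment and country as factors and the ranked baseline seizure frequency per" 28 days.
- **Protocol 9.7.5, sensitivity model with a permutation p-value:** "with treatment and pooled center (either US or ROW) as factors and the rank of baseline seizure frequency as a covariate".
- **Protocol Synopsis:** "with treatment and pooled countries as factors", with no rule for the pooling.
- **Randomisation (Protocol 9.7.1):** "Randomization for Cohort 2 will be stratified by country". SAP 3.6 says the same. Protocol section 6 places sites "in the USA, the Russian Federation (Russia), Australia, Bulgaria, Germany and Poland", which is six countries.
- **SAP 8.1, sensitivity ANCOVA:** it "will be conducted on the rank of percent change data from baseline, with treatment and pooled center (either US or ROW) as factors", and its p-value "will be determined by permutation test with seed = 123456 and 2000 iterations".
- **SAP section 10:** one declared departure from the protocol, the restriction of the primary analysis to Cohort 2.
- **Protocol Appendix 8:** the reason given for the statistical edits of Amendment 4 is that they follow changes made to the SAP, so the two texts were meant to agree.

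**The concern.** The US/ROW factor merges five of the six randomisation strata into one. Protocol 9.7.5 names country and US/ROW in consecutive paragraphs, one for the primary and one for the sensitivity model, so its text treats them as different things. The SAP promotes the sensitivity factor to primary and does not say so.

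Two things follow. First, the test that supports FDA registration and opens the fixed sequence of three key secondary endpoints has two definitions. Unless this is settled before unblinding, there will be two candidate p-values. Second, the protocol's sensitivity analysis changed the geographic factor, whereas the SAP's does not, so the SAP cannot show whether the result depends on that choice.

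Statistically, treatment is balanced within country by design, so real differences between ROW countries (in placebo response or seizure reporting, for example) do not disturb the treatment estimate. A model that ignores them still counts them as residual noise, so the standard error is too large and the test is conservative.

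**Working it through.** **1. The models side by side**

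| Analysis of the primary endpoint | Protocol 9.7.5 | SAP |
|---|---|---|
| Primary rank ANCOVA | country | US/ROW (8.1) |
| Permutation ANCOVA | US/ROW | US/ROW (8.1) |
| Multiple imputation | not described | the 8.1 model, so US/ROW (6.3) |
| Per-protocol | supportive, no separate model (9.7.2) | supportive, no separate model (5.4, 8.1) |
| Subgroup models | not described | primary model terms plus subgroup and interaction (8.3.3) |

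In the SAP, the permutation ANCOVA has the same ranks, factors and covariate as the primary model. It tests the reference distribution, not the country adjustment. The geographical-region subgroup in SAP 8.3.3 is not defined.

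**2. The plan's own power figure**

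Inputs from SAP 3.5: 178 per group, effect size 0.30, two-sided alpha 0.05, Wilcoxon test, power about 80%.

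- Normal approximation: Φ(0.30 × √(178/2) − 1.96) = Φ(2.83 − 1.96) = 80.8%.
- With Wilcoxon efficiency 3/π applied to n: 79.0%.

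The stated figure is reproduced. It uses no geographic term, so the choice of factor does not change it.

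**3. Cost in degrees of freedom**

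With 356 subjects, the US/ROW model has 4 parameters and 352 residual degrees of freedom. The six-country model has 8 parameters and 348.

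**4. Analytic check with total variance held fixed**

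Let country explain a share R² of rank variance beyond US/ROW. Take a planned standardised effect of 1.96 + 0.84 = 2.80, which is 80% power.

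- US/ROW power = Φ(0.84/√(1 − R²)); its true alpha = 2 × [1 − Φ(1.96/√(1 − R²))].
- Country power = Φ(2.80/√(1 − R²) − 1.96).

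| R² (assumed) | US/ROW power | Country power | Gain, points | US/ROW alpha |
|---|---|---|---|---|
| 0.05 | 80.6% | 81.9% | 1.4 | 4.4% |
| 0.10 | 81.2% | 83.9% | 2.7 | 3.9% |

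**5. Simulation of the rank ANCOVA**

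Assumptions, none of them in the documents:

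- 356 subjects in blocks of 4 within country, effect 0.30 SD, normal outcome with within-country SD 1, and a ranked baseline unrelated to outcome.
- Country sizes (US first) 160/70/20/40/26/40 or 90/110/20/60/26/50.
- ROW country effects either drawn at random with the stated SD (8,000 replicates) or fixed at plus or minus that size (5,000 replicates). The ranges below span both splits and both schemes.

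| ROW country effects | Power, US/ROW | Power, country | Gain, points | Trials where the models disagree on significance |
|---|---|---|---|---|
| none | 78–79% | 78–79% | none | about 0.3% |
| 0.25 SD | 77.2–77.7% | 78.0–79.0% | 0.8–1.3 | 1.0–1.4% |
| 0.5 SD | 73.2–75.9% | 78.1–79.2% | 2.5–5.2 | 2.5–5.2% |

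US/ROW alpha at 0.5 SD is 3.3–4.3%. The Monte Carlo standard error is about 0.5–0.6 points for power and 0.2–0.3 for alpha.

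A second simulation used other country shares (US 40% or 20%), a baseline related to outcome, and a spread across all six countries (3,000 runs per setting). The gain was about 1 point at a spread of 0.2 residual SD, 4–5 points at 0.4 and 10–12 points at 0.6. At 0.6, alpha was 2.4% with US/ROW and 4.8–4.9% with country.

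**6. Permutation scheme**

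Neither document says whether labels are shuffled within country. For the US/ROW model with the second split in step 5 and random effects of 0.5 SD (2,500 replicates, 400 shuffles each):

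- Unrestricted shuffling: type I error 4.0%, power 72.4%.
- Shuffling within country: type I error 5.0%, power 76.0%.

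**The case against.** The strongest reply is that Protocol 9.7.5 is the stale text. The Synopsis wording is compatible with US/ROW. The change table in Appendix 8 shows the country factor carried over from the previous log-scale ANCOVA, while the analyses newly added by Amendment 4 use US/ROW. That amendment says it follows the SAP, and Protocol 9.5.2 sends the reader to the SAP for detail. On this reading the SAP is clear and pre-specified, and one word in 9.7.5 needs correcting. This may well be right. It cannot be settled from the text, and it does not remove the need to declare the choice, reconcile 9.7.5 and give a reason for leaving the randomisation stratum out.

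On size, 0.5 SD is a large country effect. With the planning SD of 50% (Protocol 9.7.9) it is 0.5 × 50 = 25 points, more than the 15-point treatment effect. The simulation in step 5 also adds country variance on top of an SD of 1, which lowers the power level. Both points stand for the level, less so for the gain. With total SD held at 1, fixed effects gave gains of about 0.6 to 2.7 points, and random effects of 0.5 SD (first country split) still gave about 2.5 points.

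Two smaller points also have some force. The geographical-region subgroup may be finer than US/ROW, because it is added to a model that already contains that factor; it is still undefined and is not a sensitivity analysis. Changing only the primary model would also leave other efficacy analyses on US/ROW, but for CGI-I the two documents agree on US/ROW, and for responder rates the protocol names no covariates, so neither conflicts.

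**Conclusion.** The concern holds. The SAP's primary model differs from Protocol 9.7.5, departs from the randomisation stratum, is not declared in SAP section 10, and is not tested by any planned sensitivity analysis of the primary endpoint. The protocol is also inconsistent with itself, because the Synopsis speaks of pooled countries without a rule.

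This is an undeclared discrepancy between pre-specified texts, not a post hoc choice, and it carries no false-positive risk. What is at stake is which p-value is the registration test, plus a possible loss of power. That loss is nil if ROW countries are alike and about 1 point at moderate differences (0.25 SD). It is 2.5 to 5.2 points at 0.5 SD when country variance is added to the planning SD, and nearer 0.6 to 2.7 points when total variance is held fixed. All of these figures rest on assumed country sizes and effects. The textual conflict rests on no assumption. It should be fixed before unblinding.

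**What to change.** Before unblinding, either:

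1. **Preferred.** Put country in the SAP 8.1 primary rank ANCOVA, with a rule fixed on blinded data for merging very small countries. Keep US/ROW as the sensitivity model, as in Protocol 9.7.5. Align the Synopsis, Protocol 9.7.5, SAP 6.5 and SAP 8.1.
2. **If US/ROW stays primary.** Give the reason, list it in SAP section 10, correct Protocol 9.7.5, define the pooling in the Synopsis, and add a country-adjusted rank ANCOVA as a sensitivity analysis.

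In either case, state that the permutation test shuffles labels within country. No change is needed for CGI-I or the responder model.

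The cost is wording in both documents, four model degrees of freedom if all six countries enrol in Cohort 2, and one line in the permutation program. No further data or patients are needed.
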